## 1 AMENDMENTS FROM PREVIOUS VERSION(S)

### Amendment 1

Section of the SAP	Summary of change	Rationale
2	Spacing issue resolved	Proper formatting
2.1	Added text to include biopsy in assessment of TTR genetic test results. Added text to clarify that complications that will be summarized is related to transplantations. Spacing issue resolved.	Additional clarification for ease of identifying data to be analysed. Proper formatting.
5.3	Added the text “final treatment” corresponding to discontinuation of tafamidis. Added the text “Discontinuation refers to the final treatment discontinuation of tafamidis” in Figure 1. Spelling change of “analyse”	Clarification to highlight that only the last and final date of treatment discontinuation of tafamidis will be considered to identify patients in the tafamidis treated set as there could be multiple discontinuations in THAOS due to the non-interventional nature of this study. Consistency across all sections to use “analyse”.
5.4	Revised definitions of the phenotypes with consistent language used in the THAOS ad-hoc publications. Additional text added on classification of patients by liver transplant status for the	To be consistent with the new and updated definitions of phenotypes across all deliverables related to THAOS. The changes in the subgroups with liver transplant in the enrolled

PFIZER CONFIDENTIAL

	enrolled patients and the tafamidis treated patients.	set and in tafamidis treated set provides an exhaustive list of all possibilities of either having a liver transplant (prior or after) or no liver transplant.
6.1.2.2	Layout of the second paragraph changed in the form of a sentence from the previous itemized version.	To maintain consistency in formatting with sections 6.1.2.1 and 6.1.2.3.
CCI	[REDACTED]	[REDACTED]
[REDACTED]	[REDACTED]	[REDACTED]
7	Additional text and corrections on which dates and months to be used for imputing missing dates and specification of the domains for which such imputations will be applied.	To be consistent with the programming standards for imputing missing dates.
8.2	Added the text tafamidis in the last paragraph	To provide clarity that off-label usage corresponds to the study drug tafamidis.
8.2.1	Added text on discontinuation refers to both from the study drug as well as study.	To ensure completeness of summarization of discontinuation either from study drug or study.

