## 5.2 TAFAMIDIS UNTREATED

The tafamidis untreated set will include the following:

- All available data from patients who have been enrolled in THAOS, signed the informed consent and who have not received tafamidis during the THAOS study.
- All available data before receiving the first dose of tafamidis while in THAOS, for those patients who were not on tafamidis during or after initial enrollment in THAOS but then started receiving tafamidis post enrollment.

Note: Available data after a patient discontinues treatment with tafamidis will be excluded (See Figure 1)

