## 5.3 TAFAMIDIS TREATED

The tafamidis treated set will include the following:

[figure not shown]
- All available data from the enrollment date until final treatment discontinuation of tafamidis or end of follow-up in THAOS (whichever is earlier) for patients who have been enrolled in THAOS, signed the informed consent and who were on tafamidis treatment on or prior to the date of enrollment in THAOS.
- All available data from first dose of tafamidis until final treatment discontinuation of tafamidis or end of follow-up in THAOS (whichever is earlier) for patients who were not on tafamidis at the time of enrollment in THAOS but subsequently initiated treatment with tafamidis.

Note: A patient can be considered part of both the tafamidis untreated and tafamidis treated sets if the patient initiated treatment with tafamidis after beginning participation in THAOS.

The below schematic will help to better understand the patient population to be analysed:

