**Figure 1 Schematic of Patient Populations to be analysed**

**Patient population:** Tafamidis Treated (includes data in orange)  
 Tafamidis Untreated (includes data in blue; excludes data after start of Tafamidis treatment [orange] including any data after discontinuation of Tafamidis [dashed line] if patient remains in follow-up)

T is denoted as Tafamidis

Discontinuation refers to the final treatment discontinuation of tafamidis

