#### **6.2.1 Survival**

Survival will be analysed as time from enrollment or first dose of tafamidis, for the untreated and tafamidis treated set respective until the time of death. Patients who are still alive at the end of the analysis period (start of tafamidis or end of follow-up in THAOS for the untreated set or last dose of tafamidis in the tafamidis treated set) will be censored.

CCI [Redacted]

[Redacted]

[Redacted]

[Redacted]

- [Redacted]
- [Redacted]
- [Redacted]

CCI [Redacted]

[Redacted]

[Redacted]

[Redacted]

PFIZER CONFIDENTIAL

[Redacted]

CCI

[Redacted]

[Redacted]

[Redacted]

CCI

[Redacted]

[Redacted]

[Redacted]

[Redacted]

[Redacted]

CCI

[Redacted]

[Redacted]

PFIZER CONFIDENTIAL

[Redacted]

CCI [Redacted]

CCI [Redacted]

[Redacted]

[Redacted]

[Redacted]

[Redacted]

[Redacted]

[Redacted]

- [Redacted]
- [Redacted]
- [Redacted]
- [Redacted]

PFIZER CONFIDENTIAL

[Redacted]

CCI [Redacted]

[Redacted]

[Redacted]

[Redacted]

- [Redacted]
- [Redacted]
- [Redacted]
- [Redacted]
- [Redacted]
- [Redacted]

[Redacted]

- [Redacted]
- [Redacted]

[Redacted]

[Redacted]

CCI [Redacted]

[Redacted]

[Redacted]

[Redacted]

CCI [REDACTED]

CCI [REDACTED]

CCI [REDACTED]

[REDACTED]

[REDACTED]

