### **Echocardiogram**

For Echocardiogram, summary statistics for the baseline will be provided for:

- Left atrium
- Aortic root
- LV septum
- LV posterior wall

- LV diastolic diameter
- LV systolic diameter
- LV ejection
- RV free wall thickness
- Quantitative LV end systolic volumes
- Quantitative LV end diastolic volumes
- Transmitral E wave peak velocity
- E wave deceleration time
- Transmitral A wave Peak velocity
- Peak tricuspid regurgitation velocity
- Derived peak pulmonary artery systolic pressure
- Septal and Lateral Peak E, A, S
- Stroke volume
- Cardiac output

Also for the following parameters corresponding to Echocardiogram, summaries will be provided at baseline:

- Value abnormalities
- Types of value abnormalities
- Respiratory variation
- Sparkling

Echocardiogram summaries will be performed for the following sets: tafamidis untreated set with predominantly cardiac or mixed phenotype at enrollment, tafamidis treated set with predominantly cardiac or mixed phenotype at enrollment, CCI [REDACTED] and either predominantly cardiac or mixed phenotype at enrollment, tafamidis treated set for patients who switched from predominantly neurologic to mixed phenotype and tafamidis untreated set for patients who switched from predominantly neurologic to mixed phenotype.

*Note: For all the above safety events (Concomitant medications, hospitalization, AE/SAE, Deaths, Laboratory, Vitals and ECG) all events collected till last tafamidis dosing date +28 days will be summarized for the tafamidis treated set and its associated sub-sets.*

CCI [REDACTED]  
[REDACTED]  
[REDACTED]  
[REDACTED]  
[REDACTED]  
[REDACTED]

PFIZER CONFIDENTIAL

CCI [Redacted]

CCI [Redacted]

[Redacted]

[Redacted]

[Redacted]

[Redacted]

[Redacted]

[Redacted]

[Redacted]

[Redacted]

PFIZER CONFIDENTIAL

[Redacted]

CCI [Redacted]

[Redacted]

CCI [Redacted]

[Redacted]

- [Redacted]
- [Redacted]
- [Redacted]
- [Redacted]
- [Redacted]
- [Redacted]
- [Redacted]
- [Redacted]
- [Redacted]
- [Redacted]
- [Redacted]

[Redacted]

CCI [Redacted]

[Redacted]

[Redacted]

CCI [REDACTED]

[REDACTED]  
[REDACTED]  
[REDACTED]

[REDACTED]  
[REDACTED]

[REDACTED]

[REDACTED]  
[REDACTED]  
[REDACTED]

[REDACTED]

[REDACTED]  
[REDACTED]  
[REDACTED]

[REDACTED]

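### Treated-set survival runs to the final tafamidis stop, so an off-drug gap counts as survival time only if the patient lives to restart, which raises estimated survival on tafamidis

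*SAP*

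**What the plan says.** **End of treated time.** For patients who start tafamidis after enrollment, SAP 5.3 takes "All available data from first dose of tafamidis until final treatment discontinuation of tafamidis or end of follow-up in THAOS (whichever is earlier"). For those already on drug it takes "All available data from the enrollment date until final treatment discontinuation of tafamidis or end of follow-up in THAOS (whichever is earlier"). The text under Figure 1 adds: "Discontinuation refers to the final treatment discontinuation of tafamidis". The Amendment 1 log explains why only the last stop counts: "there could be multiple discontinuations in THAOS due to the non-interventional nature of this study".

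**Survival.** SAP 6.2.1 measures time to death. Patients alive at the end of the analysis period, which for treated patients is the "last dose of tafamidis in the tafamidis treated set) will be censored". That section gives no lag after the last dose.

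**Post-stop data.** The note in SAP 5.2 removes them from the untreated set as well: "Available data after a patient discontinues treatment with tafamidis will be excluded".

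**28-day note.** At the end of the Echocardiogram text in SAP 8.2.6, "all events collected till last tafamidis dosing date +28 days will be summarized for the tafamidis treated set". The domains listed there include Deaths but not the survival analysis.

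**Where deaths are displayed.** In the visible text, the mortality plots in 8.2.6 cover the treated and untreated sets and their subgroups. The Survival row of the 8.2.8 table has no mark under All enrolled. The Deaths paragraph of 8.2.6 does count deaths among all enrolled patients.

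**Exposure.** The duration formula in 8.2.6 adds up only the days on which tafamidis was taken, so it leaves gaps out.

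**The concern.** A stop becomes final only when no restart follows, so the rule uses future information to decide whether off-drug time belongs to the treated set. Two hypothetical patients show this:

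- One takes tafamidis for 1 year, stops for 2 years, restarts and is followed to year 4. All 4 years count as treated survival, including the 2 off drug.
- The other takes tafamidis for 1 year, stops, and dies 2 years later without restarting. This patient is censored at year 1, or at year 1 plus 28 days. The death is in neither the treated nor the untreated curve.

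Completed gaps therefore enter the risk set as time in which nobody could have died. This is immortal time, created by the definition itself. The SAP is also inconsistent on the point, because exposure duration leaves out a gap that the survival time scale keeps.

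SAP section 2 says the data will give information on the effect of tafamidis on survival, in a post-authorization safety study committed to EMA. A descriptive curve with event-free time built into it still misdescribes survival on the drug. The visible SAP has no sensitivity analysis for this rule.

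**Working it through.** The documents give no sample size, event count, mortality rate, stop rate, restart rate or gap length, so there is no plan figure to reproduce. **Every rate below is an assumption.** The only scale available is Protocol 7.1, which puts death in ATTR-PN at a mean of 10 to 15 years from first symptoms. That suggests hazards of 1/10 and 1/15 per year.

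**Step 1. What a gap does.** Take 100 patients with hazard 0.10/year on and off drug, all stopping at year 2 and due to restart at year 3 (exaggerated, to show the mechanism).

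- Alive at the stop: 100 × exp(−0.2) = 81.87.
- Deaths in the gap year: 81.87 × (1 − exp(−0.1)) = 7.79.
- Of these, within 28 days: 81.87 × (1 − exp(−0.1 × 28/365.25)) = 0.63.
- The other 7.17 deaths are censored. The 81.87 − 7.79 = 74.08 who restart contribute a full year without events.

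**Step 2. Closed form.** Let λ be the on-drug hazard and g the share of analysed person-time that is completed gap. Events arise only in on-drug time, so observed hazard = λ(1 − g), and 5-year survival = exp(−5λ(1 − g)).

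| g | λ = 0.10 | λ = 1/15 |
|---|---|---|
| 0 (true on-drug) | 60.7% | 71.7% |
| 2% | 61.3% | 72.1% |
| 5% | 62.2% | 72.9% |
| 10% | 63.8% | 74.1% |
| 20% | 67.0% | 76.6% |

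**Step 3. Simulation.** On/off/death model, 60,000 patients per scenario, 8 years' follow-up, 5-year Kaplan-Meier. Rows shown have λ = 0.10, for which true on-drug survival is exp(−0.5) = 60.7%. The SAP column runs to last dose plus 28 days. The on-drug-interval and first-stop columns use the same 28-day lag, so they compare like with like.

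| Off/on hazard | Stops per year | Restart | SAP rule | On-drug intervals | First stop | All follow-up | Gap share | Deaths in no curve |
|---|---|---|---|---|---|---|---|---|
| 0.5 | 20% | gap about 1 y | 64.7% | 60.9% | 61.1% | 62.8% | 12.9% | 7.3% |
| 1 | 10% | gap about 1 y | 62.4% | 60.5% | 60.6% | 60.6% | 6.4% | 7.1% |
| 1 | 20% | gap about 1 y | 64.1% | 60.5% | 60.5% | 60.6% | 12.0% | 12.7% |
| 2 | 10% | gap about 1 y | 61.8% | 60.2% | 60.1% | 58.3% | 5.5% | 12.2% |
| 4 | 5% | gap about 1 y | 60.6% | 60.0% | 59.9% | 57.5% | 2.2% | 10.4% |
| 0.5 | 10% | none | 60.9% | 60.9% | 60.9% | 64.3% | 0% | 17.8% |
| 1 | 10% | none | 61.1% | 61.1% | 61.1% | 61.1% | 0% | 26.9% |
| 2 | 10% | none | 60.3% | 60.3% | 60.3% | 55.2% | 0% | 36.4% |

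The closed form agrees: with g = 6.4%, exp(−0.5 × 0.936) = 62.6%, against 62.4% simulated.

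**Step 4. Reading the table.**

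- With restarts, the SAP rule exceeds the on-drug-interval estimate in every scenario run, by 0.6 points (60.6 − 60.0) to 3.8 points (64.7 − 60.9). This includes scenarios where off-drug risk equals or is below on-drug risk.
- With no restarts the two agree, although many deaths enter no curve. The gap rule is therefore what produces the bias here.
- A low restart rate alone does not make it negligible. In the runs with few restarts (λ = 0.10, 10% stops per year) the excess was still 1.3 points (61.3 − 60.0) to 3.2 points (63.8 − 60.6), because the gaps that do end in a restart can be long. It goes to zero as restarts disappear or as gaps shrink to the length of the lag.

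**The case against.** The best defence is that survival is filed as a safety endpoint, where on-treatment censoring is legitimate. SAP section 4 says there are no hypotheses and all analyses are descriptive, and no test of treated against untreated is planned. The SAP says only that several discontinuations could occur, not how often, so the effect may be trivial. This stands as a limit on size. It does not justify the rule, because on-treatment censoring would end at-risk time when the drug stops, whereas this rule keeps off-drug time for survivors only.

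A reader might infer four stronger things that the documents do not support:

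- **That the excluded post-stop deaths necessarily inflate the curve too.** They bias on-drug survival only if stopping is related to prognosis, and the documents do not show that. In the no-restart rows, 17.8% to 36.4% of deaths enter no curve without any excess over the on-drug estimate.
- **That the overstatement is much larger.** Against all follow-up after first dose, the SAP rule was higher by 0.5 to 11.2 points in the runs with restarts. That is a different estimand. The larger differences come mainly from assuming higher mortality off drug, and the sign can reverse: with off-drug hazard halved and no restarts, all follow-up gives 64.3% against 60.9%.
- **That these deaths vanish from the report.** They remain in the all-enrolled death summary, by cause and ATTR relatedness.
- **That the untreated curve is a clean comparator.** It has no gap time, but its patients are censored at the start of tafamidis, which may also depend on prognosis.

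**Conclusion.** The concern holds for the gap rule. Under SAP 5.3, Figure 1 and 6.2.1, off-drug time enters treated survival only if the patient survives it. This raises estimated on-tafamidis survival whenever gaps longer than the tail occur, with no need for higher off-drug risk. Under the assumed rates with restarts, the like-for-like overstatement at 5 years is about 0.6 to 4 points. It is near zero if restarts are very rare or gaps short. The true size cannot be found from the documents.

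Deaths beyond any 28-day tail enter no Kaplan-Meier curve. If 6.2.1 is read literally, deaths within 28 days of the last dose are outside the treated curve as well. The loss of post-stop deaths adds bias to on-drug survival only if stopping depends on prognosis.

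**What to change.** In SAP 6.2.1:

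1. **On-treatment curve.** Censor at the first stop plus a fixed lag (for example 28 days), counting deaths inside the lag. Alternatively, split at-risk time by the logged tafamidis start and stop dates with the same lag. Label the curve as survival while on tafamidis. The lag must apply to everyone who stops: censoring at the stop date only for interruptions over 28 days again uses the future, and it lowered 5-year survival by about 0.3 points at 15% stopping per year.
2. **Sensitivity curve.** Follow from first dose (or enrollment if already on drug) to death or last known alive. Label it as including off-drug time and time on other therapies or after transplant.
3. **Reconcile and report.** Make the last-dose censoring in 6.2.1 agree with the 28-day note in 8.2.6. Report the number and length of gaps and the number of post-stop deaths.

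The data are already collected: SAP Table 2 includes a tafamidis log with start and stop dates, and deaths are recorded independently of visits. The cost is SAP wording and one more Kaplan-Meier run. The drawbacks are fewer events in the on-treatment curve if it is censored at first stop, and an all-follow-up curve that mixes in later therapies.

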**Figure 1 Schematic of Patient Populations to be analysed**

**Patient population:** Tafamidis Treated (includes data in orange)  
 Tafamidis Untreated (includes data in blue; excludes data after start of Tafamidis treatment [orange] including any data after discontinuation of Tafamidis [dashed line] if patient remains in follow-up)

T is denoted as Tafamidis

Discontinuation refers to the final treatment discontinuation of tafamidis

## 5.4 SUBGROUPS

Subsets/subgroups of the above population, based on patient characteristics, will be used for certain outcomes. Descriptions of key subgroups from THAOS are provided below:

### Predominantly Cardiac Phenotype

Predominantly cardiac phenotype includes:

1) Wild type ATTR-CM patients (symptomatic or not) with or without neurologic or gastrointestinal symptoms as follow:

- Neurologic or gastrointestinal (GI) symptoms (erectile dysfunction, constipation, and carpal tunnel) of any severity related or not to ATTR; OR
- Neurologic or gastrointestinal (GI) symptoms (other than erectile dysfunction, constipation, and carpal tunnel) of any severity if unrelated to ATTR; OR
- Neurologic or gastrointestinal (GI) symptoms (other than erectile dysfunction, constipation, and carpal tunnel) of mild severity if related or possibly related to ATTR; AND

- CCI [REDACTED]  
[REDACTED]

Cardiac and neurologic symptoms do not need to be ongoing at a given visit to be included for phenotyping.

2) Symptomatic ATTRv amyloidosis participants that fulfil the following criteria:

- Presence of abnormal electrocardiogram (ECG) due to rhythm disturbance, heart failure, or dyspnea) of any severity; AND
- Absence of neurologic or gastrointestinal (GI) symptoms (ATTR unrelated, related or possibly symptoms) reported in medical history; AND
- CCI [REDACTED]  
[REDACTED]

### **Predominantly Neurologic Phenotype**

Predominantly neurologic phenotype includes:

- Symptomatic ATTRv patients with neurologic or GI symptoms of any severity (neurologic and GI symptoms needs to be ongoing and definitely ATTR amyloidosis related); AND
- Absence of abnormal ECG due to rhythm disturbance, heart failure, or dyspnea;

A mPND score  $\geq$  I will be considered a neurologic symptom in this subgroup when reported. Symptomatic patients with missing neurologic and GI symptoms but with a

CCI score  $\geq$  I and without abnormal ECG CCI [REDACTED]  
[REDACTED]

### **Mixed Phenotype**

Mixed phenotype includes:

PFIZER CONFIDENTIAL

## 1) Wild type participants with:

- Any neurologic or GI symptoms excluding Erectile dysfunction/constipation/carpal tunnel syndrome of moderate or severe intensity that are classified as related or possibility related to ATTR;

A mPND score  $\geq$  I will qualify the participant as mixed phenotype independent of the presence of other neurological or GI symptoms.

## 2) Symptomatic ATTRv amyloidosis participants that fulfil the following criteria:

- Abnormal ECG due to rhythm disturbance, heart failure, or dyspnea, AND
- Any ongoing neurologic or GI symptoms including erectile dysfunction, constipation, carpal tunnel syndrome of any severity, AND / OR
- A mPND score  $\geq$  I

Mixed phenotype will not be combined with any other phenotype when analyzing the data.

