## **9.5. Study Size**

THAOS has been open since 2007. There is no set number of patients who will be enrolled in the survey. Patients will be enrolled from different countries around the world. All patients who take part in this survey will be followed until the survey is declared complete by Pfizer (currently estimated to be the year 2023) or as long as they are able to participate, or until they withdraw consent to participate.

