### **4 HYPOTHESES AND DECISION RULES**

There are no hypotheses associated with this survey. All analyses will be descriptive.

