**\*Changes of phenotype**

Under the assumption that phenotype-related symptoms do not truly disappear, but are only possibly masked or temporarily resolved, once determined, phenotype classification

PFIZER CONFIDENTIAL

will be carried forward to future visits even if there are no available symptom data at the subsequent visit. Patients classified as predominantly cardiac or predominantly neurologic at a given visit will continue to be classified as such at subsequent visits unless the patient develops additional symptoms warranting a re-classification to mixed phenotype. Missing data on prior visit will disqualify re-classification (participant must have data entered in the same measure to allow comparison and reclassification). The mixed phenotype is a persistent state, i.e, once a patient is classified as mixed phenotype at a given visit, then that patients remains mixed at all subsequent visits.

For those patients who initiated treatment with tafamidis after beginning participation in THAOS, phenotype treatment baseline will be the most recent phenotype classification prior to first dose.

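### For hereditary (ATTRv) patients the phenotype rules disagree on whether unrelated symptoms count, so the permanent mixed class takes in an unknown share of conversions that are not disease progression

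*SAP*

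**What the plan says.** SAP section 5.4 sets the mixed rule for symptomatic ATTRv patients. On the cardiac side it asks for "Abnormal ECG due to rhythm disturbance, heart failure, or dyspnea, AND". On the other side it asks for "Any ongoing neurologic or GI symptoms including erectile dysfunction, constipation, carpal tunnel syndrome of any severity", joined by AND / OR to an mPND score of I or above. Neither side mentions relatedness to ATTR amyloidosis. The ATTRv mixed row of Table 3 does not mention it either. That row accepts cardiac findings whether ongoing or past, and its mPND cell allows a score of 1 or a missing score.

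The neighbouring rules do use relatedness. For predominantly neurologic ATTRv, "neurologic and GI symptoms needs to be ongoing and definitely ATTR amyloidosis related". For wild-type mixed, the symptoms must be "of moderate or severe intensity that are classified as related or possibility related to ATTR", and an unrelated symptom leaves a wild-type patient in the cardiac class.

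For predominantly cardiac ATTRv, the text requires that no neurologic or GI symptom be on record, and it names unrelated symptoms explicitly. The corresponding row of Table 3 excludes only related or possibly related ones.

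Under Changes of phenotype, "once a patient is classified as mixed phenotype at a given visit, then that patients remains mixed at all subsequent visits". The stated ground for carrying classes forward is "Under the assumption that phenotype-related symptoms do not truly disappear". Re-classification needs additional symptoms, and it is blocked when the same measure is missing at the prior visit.

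**The concern.** Two programmers working from section 5.4 and Table 3 could assign different phenotypes to the same ATTRv patient. On the text, one mild unrelated complaint in a patient with a cardiac finding is enough for mixed. The class is then kept for good, on an argument about phenotype-related symptoms that does not extend to unrelated ones.

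There are two routes into the converter groups, and both lack an attribution rule:

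- **Cardiac to mixed** turns on the neurologic/GI condition. It feeds the summaries of post-baseline symptoms (SAP 8.2.4).
- **Neurologic to mixed** turns on the cardiac condition. It feeds the same symptom summaries and also the converter ECG and echocardiogram groups (SAP 8.2.6).

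The second route also affects the off-label subgroup, defined as patients who are neither cardiac nor mixed at the first 80/61 mg dose. A neurologic patient who becomes mixed on an unrelated dyspnoea entry leaves that subgroup, which serves a stated objective (SAP 2.2).

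**Working it through.** **1. Text against table.** Take a symptomatic ATTRv patient with a qualifying cardiac finding and one ongoing neurologic or GI symptom rated unrelated. Read the AND / OR in the text as permitting OR.

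| mPND | Section 5.4 text | Table 3 |
|---|---|---|
| Recorded below I | Mixed (cardiac is barred) | Cardiac only (mixed row lists 1 or missing) |
| Missing | Mixed (cardiac is barred) | Cardiac row and mixed row both met |
| I or above | Mixed | Mixed |

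The sources disagree in the first two rows, and in the second Table 3 also gives two classes. No order of precedence is visible. mPND can be missing because assessments are recommended but not required (SAP 2.1). Part of the cardiac text is redacted, but that does not change the table: the visible condition already excludes this patient from cardiac. The mixed text and the ATTRv mixed row show no redaction.

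**2. Possible size.** The plan states no conversion rate and no rate of unrelated symptoms, so there is no figure of its own to reproduce. Everything in steps 2 to 4 is illustration. Let p be the assumed chance, per annual visit and independent between visits, that a stable patient records a new unrelated qualifying entry. Because mixed is permanent, the chance of having been converted by visit k is 1 − (1 − p)^k. The SAP's visit windows run to Year 12.

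| p | k = 5 | k = 12 |
|---|---|---|
| 1% | 4.9% | 11.4% |
| 2% | 1 − 0.98^5 = 9.6% | 21.5% |
| 5% | 1 − 0.95^5 = 22.6% | 46.0% |
| 10% | 41.0% | 71.8% |

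On the Table 3 reading, an unrelated neurologic or GI symptom can convert a cardiac patient only when mPND is missing. With mPND missing at an assumed share m = 30% of visits, p becomes p × m:

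- p = 2%: 1 − (1 − 0.006)^5 = 3.0% at 5 visits and 7.0% at 12.
- p = 5%: 1 − (1 − 0.015)^5 = 7.3% at 5 visits and 16.6% at 12.

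This reduction applies to the cardiac-to-mixed route. A neurologic patient whose mPND is 1 or missing already satisfies the mPND cell of the mixed row. The prior-visit-data rule would lower all these figures by an unknown amount.

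**3. Share of converters.** Let q be the assumed per-visit chance of true progression. The share of converters whose conversion rests on an unrelated symptom only is p(1 − q) / [1 − (1 − p)(1 − q)].

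- p = 2%, q = 10%: 0.018 / 0.118 = 15%.
- p = q = 5%: 0.0475 / 0.0975 = 49%.
- p = 10%, q = 2%: 0.098 / 0.118 = 83%.

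**4. Is growth with follow-up a sign of artefact?** With p = 0 and q = 5%, conversions rise from 14.3% at 3 visits to 33.7% at 8. With p = 5% and q = 0 the figures are identical. Growth with visits cannot separate the two sources.

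**The case against.** A reader might infer that counted conversions track the number of visits and not the disease. The documents do not support that. Step 4 shows that true progression accumulates in the same way, and the unrelated share in step 3 is set entirely by assumption.

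A reader might also expect survival, adverse-event and death results to be distorted by conversion. Those summaries use phenotype at enrollment. The contradictory rules also assign that baseline class, but later conversions do not enter. Echocardiogram data are summarised at baseline only, so false conversions change who is in the converter group without creating apparent echo progression.

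Other points in the plan's favour:

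- The cardiac text names unrelated symptoms, so counting them for ATTRv may be partly deliberate. If so, the Table 3 cardiac row is wrong and the difference from wild-type needs a reason.
- "There are no hypotheses associated with this survey. All analyses will be descriptive", and the protocol says "There is no set number of patients who will be enrolled in the survey". No decision rule depends on conversions, and no visible output compares conversion rates between treated and untreated patients. The SAP's change log mentions phenotype shift tables, but that area is redacted.
- Post-baseline symptoms in converters are already split by relatedness, so dilution would be partly visible. The split does not change who is in the group and does not reach ECG.
- Making a related-only rule the primary one would have side effects. A patient with related neuropathy and unrelated dyspnoea would no longer be mixed, yet could not be neurologic, because that class excludes dyspnoea whatever its cause.

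These points limit the consequence and argue against simply replacing the rule. They do not remove the contradiction between text and table.

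**Conclusion.** The point holds as a contradiction in the ATTRv rules together with an unmeasured mixture in the converter groups. That text and table disagree needs no assumption. How many stable patients convert is unknown. The range of 10–23% by 5 visits on the text, or about 3–7% on Table 3, rests on an assumed 2–5% per visit, independence between annual visits and, for Table 3, mPND missing at 30% of visits. What is affected is the converter symptom and ECG summaries, membership of the converter echo groups, and the off-label subgroup. This is worth correcting before the final report, but it does not show that the conversion results are mainly artefact.

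**What to change.** In SAP 5.4 and Table 3:

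1. Reconcile the cardiac text, the mixed text and Table 3 so that every ATTRv patient falls in exactly one class. Cover a recorded mPND below I, and say how an unrelated cardiac finding is treated in both the neurologic and the mixed rules.
2. State whether relatedness is required for ATTRv mixed, at baseline and for re-classification.
3. Derive conversions two ways: on any symptom, and on definitely or possibly related symptoms only. Show the converter outputs and the off-label count under both.
4. Report conversions per patient-year of follow-up.

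The cost is SAP wording, a second derivation of the phenotype variable and repeat runs of the affected tables. Symptom relatedness is already collected and summarised (SAP 8.2.4). The downside is that relatedness is rated by the investigator. The related-only version may therefore miss some true conversions or count them later, and some patients may change class. Showing both versions makes the extent visible.
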